9.6.1.2. Annual surveillance reports

Annual surveillance reports will be developed during the period when live-birth pregnancies are identified in the feasibility assessment (2021-2024; including pregnancies identified during the period July 1, 2021- June 30, 2023). Annual surveillance reports will continue to be developed as data accrue during the period of the cohort study (2025-2028; including pregnancies identified during the period July 1, 2021-June 30, 2026) or during period of the descriptive analysis (2025; including only pregnancies identified during the period July 1, 2021- June 30, 2023), as relevant.

9.7. Data analysis

Whenever possible, publicly available Sentinel analytic tools will be used for the distributed analyses; these are the same tools used by FDA for similar analyses. Modifications to the tools may be needed to meet study objectives, in which case the SAS programming data quality assurance (QA) Standard Operating Procedures (SOP) will be followed (see Section 9.8). All statistical calculations will be done in SAS 9.2 or higher.

214420 (EPI-ZOSTER-039 VS US DB) Protocol Amendment 2 Final

9.7.1. Characterization of Use of HZ/su and IC Conditions During Pregnancy

Annual descriptive analyses to estimate the counts of HZ/su exposed pregnancies among women with IC conditions will be performed. Data from the first two years will be used to determine the feasibility of a full-scale cohort study (see Section 9.6.1.1). Analyses will be performed in the cohort of pregnant women aged 18 to 49 years diagnosed with IC conditions meeting health plan enrollment (medical and pharmacy benefits) inclusion criteria. The analysis will be conducted for pregnancies resulting in live births. The counts of pregnancies exposed to HZ/su overall and in each trimester (including a 30-day pre-pregnancy period) will be estimated. Counts of pregnancies unexposed to HZ/su will be tabulated by maternal age, calendar year of pregnancy outcome, and IC condition. Similarly, counts of women of childbearing age (18 to 49 years) exposed to HZ/su with IC conditions will be estimated.

9.7.2. Cohort Study

If the feasibility assessment (Section 9.6.1.1) identifies that the number of HZ/su-exposed pregnancies is equal to or above the target number of exposed pregnancies, a subsequent cohort study will be conducted.

Infant/birth outcomes and pregnancy complications will be assessed among eligible live birth pregnancies linked to infant records. Pregnancy outcomes will be assessed in the population of all pregnant women meeting eligibility criteria.

Propensity scores and matching will occur within each Data Partner. Potential confounders are described in Section 9.3.3. The methodology will be described in detail in the Statistical Analysis Plan (SAP).

9.7.2.1. Primary Objective and Secondary Objective 1

The Mantel-Haenszel Chi-square test or Fisher exact test (univariate analysis), wherever appropriate, will be employed to compare the prevalence of the primary outcome (MCMs) between eligible live birth pregnancies among women with IC conditions who were vaccinated with HZ/su during pregnancy and those who were not vaccinated with HZ/su during pregnancy. Multivariable conditional logistic regression will be conducted to adjust for potential residual confounding after matching if there is statistical significance in univariate analysis. In addition, the prevalence of MCMs and their associated 95% CIs will be calculated among women with IC conditions who were exposed to HZ/su during pregnancy versus the corresponding matched women who were not exposed to HZ/su during pregnancy. All analyses will be stratified by stage of pregnancy (pre-pregnancy, first trimester, second trimester, third trimester).

Similar methods will be used for each of the secondary infant/birth outcomes (e.g., preterm birth, SGA, LBW, NICU admission, neonatal death).

9.7.2.2. Secondary Objective 2

Pregnancy outcomes will be compared between eligible pregnancies among women with IC conditions who were vaccinated with HZ/su during pregnancy and those who were not vaccinated with HZ/su during pregnancy. Univariate and multivariable statistical analyses will be performed as stated in the primary objective and secondary objective 1 (Section 9.7.2.1) for all outcomes. The prevalence of the pregnancy outcomes (live birth, stillbirth, and spontaneous abortion) and pregnancy complications (placental abruption, preeclampsia and eclampsia) and their 95% CIs will be calculated between the two groups of women. All analyses will be stratified by stage of pregnancy (pre-pregnancy, first trimester, second trimester, third trimester).

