Wherever appropriate, the Mantel-Haenszel Chi-square test or Fisher exact test (univariate analysis) will compare the prevalence of each infant/birth outcome (MCMs and secondary outcomes of interest) between eligible live birth pregnancies among women with IC conditions who were vaccinated or not vaccinated with HZ/su during pregnancy. Multivariable conditional logistic regression will be conducted to adjust for potential residual confounding after matching if there is statistical significance in univariate analysis. In addition, the prevalence of each outcome and their associated 95% confidence intervals (CIs) will be calculated among women with IC conditions who were exposed to HZ/su during pregnancy versus corresponding matched women who were not exposed to HZ/su during pregnancy. All analyses will be stratified by stage of pregnancy (pre-pregnancy, first trimester, second trimester, third trimester). Similar analyses will be conducted for pregnancy complications and outcomes among all eligible pregnancies.

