8. RESEARCH QUESTION AND OBJECTIVES

The study will address the question of whether there is an increased risk of MCMs and additional infant/birth and pregnancy outcomes among women between 18 and 49 years of age with IC conditions exposed to HZ/su during pregnancy.

² Self-calculation

214420 (EPI-ZOSTER-039 VS US DB)
Protocol Amendment 2 Final

Primary objective:

1. Evaluate the prevalence of MCMs (as defined in Section 9.3.2.1.1) among live births from women with IC conditions exposed to HZ/su compared to those not exposed to HZ/su during pregnancy.

Secondary objectives:

- 1. Assess the prevalence of additional infant/birth outcomes (preterm birth, small for gestational age (SGA), low birthweight (LBW), neonatal intensive care unit (NICU) admission, neonatal death) among live births in women with IC conditions exposed to HZ/su versus those not exposed to HZ/su during pregnancy.
- 2. Assess the prevalence of pregnancy outcomes (livebirth, stillbirth and spontaneous abortion) and pregnancy complications (placental abruption, preeclampsia and eclampsia) among livebirth and non-livebirth pregnancies in women with IC conditions exposed to HZ/su versus those not exposed to HZ/su during pregnancy.

A feasibility assessment will be conducted (see Section 9.6.1.1). If the feasibility assessment determines that it is not possible to identify an adequate number of exposed live birth pregnancies among women with IC conditions for a cohort study, a descriptive analysis will be conducted. This analysis will describe the prevalence of infant and pregnancy outcomes among exposed and unexposed pregnancies with IC conditions, with no statistical comparisons performed (see Section 9.7.3).

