For analyses evaluating pregnancy outcomes (live birth, non-live births [stillbirth and spontaneous abortion]) and pregnancy complications (placental abruption, preeclampsia and eclampsia) (Secondary Objective 2), the cohort will include pregnancies resulting in a live birth and non-live birth (stillbirth), or spontaneous abortion.

For all analyses, the unit of analysis is a pregnancy episode.

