9.2.1.3. Comparison (Unexposed) Group

Unexposed pregnancies among women with IC conditions who were not vaccinated with HZ/su (i.e., not receiving at least one dose of HZ/su during pregnancy) will be selected as a comparator with a 3:1 matching ratio to the pregnancies among women with IC conditions who were vaccinated with at least one dose of HZ/su (exposed pregnancies). This matching ratio of 1:3 was chosen because it is feasible, reduces bias and increases precision. Matching will be conducted separately for the eligible cohort of live birth pregnancies linked to an infant (Primary Objective and Secondary Objective 1 cohort) and among the cohort of all eligible live birth and non-live birth pregnancies (Secondary Objective 2 cohort).

We will monitor and evaluate the 1:3 matching plan during the feasibility assessment to see how the matching plan performs.

If the proposed matching plan performs poorly in practice (i.e., many unmatched HZ/su-exposed pregnancies would be excluded), we propose the following alternative matching plans:

- a. Exact match strategies:
 - Exactly match on DP, combined primary IC condition categories, maternal age (± 10 years), start date of the pregnancy period (± 120 days)
 - Exactly match on DP, combined primary IC condition categories, start date of the pregnancy period (± 120 days) and put age in the propensity score
- b. Propensity match strategies: Nearest neighbor matching with caliper width at 0.02, 0.03, 0.04, 0.05, 0.1 and 0.2 between propensities of the unexposed HZ/su and the HZ/su exposed

We will consider reducing the matching ratio of HZ/su-exposed to unexposed to 1:2 or 1:1 if the desired sample size cannot be achieved even with the relaxed matching plan. The corresponding sample size for 1:2 ratio will be 2436 (812 exposed and 1624 unexposed) and 2216 for 1:1 ratio (1108 exposed and 1108 unexposed) when maintaining the other assumptions (i.e., 90% power, 3% MCM prevalence, a type 1 error of 0.05 and a target risk ratio of 2.0).

[figure not shown]
The unexposed pregnancies must be pregnant/reached the week of gestational age of the exposed pregnancy (i.e., when exposure occurred) without an adverse event (i.e., spontaneous abortion or stillbirth).

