9.3.2.2. Pregnancy Complications and Outcomes (Secondary Objective 2)

The pregnancy outcomes to be evaluated include live birth, non-live birth (stillbirth, and spontaneous abortion). A stillbirth is defined as a spontaneous (non-deliberate) fetal death that occurs at or after 20 weeks' gestation but prior to delivery. A spontaneous abortion is defined as a spontaneous (non-deliberate) embryonic or fetal death that occurs prior to 20 weeks' gestation. Placental abruption (ICD-10-CM O45.X) will be identified by searching the mother's claims from 20 weeks gestation through the date of delivery. Preeclampsia and eclampsia (ICD-10-CM O11.X, O14.X, O15.X) will be identified by searching the mother's claims from 20 weeks gestation through the date of delivery. A prior study conducted at one U.S. hospital found that the sensitivity of preeclampsia and eclampsia inpatient codes are generally low, however the PPV and specificity were high [Labgold, 2021].

Pregnancy outcomes will be identified in claims data through diagnosis and procedure codes (Appendix E. Live Birth Diagnosis and Procedure Codes and Appendix H. Spontaneous Abortion and Stillbirth Codes). Pregnancy episodes resulting in a live birth will be identified using validated algorithms (see Section 9.2.1.1) that have been used in Sentinel and non-Sentinel projects [Andrade, 2012; Andrade, 2016; Johnson, 2013; Sentinel Initiative, 2018]. Pregnancy episodes ending in a non-live birth pregnancy outcome will be identified using algorithms developed through Sentinel and non-Sentinel (e.g., VSD) projects [Andrade, 2021; Naleway, 2021].

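### Section 9.7.2 places pregnancy complications in linked live births, against the all-pregnancies cohort set elsewhere; for doses after 20 weeks the search window also takes in pre-dose events

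*Protocol*

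**What the plan says.** Section 9.7.2 divides the outcomes between two populations. Of the first it says: "Infant/birth outcomes and pregnancy complications will be assessed among eligible live birth pregnancies linked to infant records". Of the second: "Pregnancy outcomes will be assessed in the population of all pregnant women meeting eligibility criteria". Complications are therefore grouped with the infant outcomes.

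Elsewhere the protocol groups them with the pregnancy outcomes:

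- Secondary Objective 2 (Section 8) assesses abruption, preeclampsia and eclampsia "among livebirth and non-livebirth pregnancies in women with IC conditions exposed to HZ/su versus those not exposed to HZ/su during pregnancy".
- Section 9.2.1 names the same three complications and says that "the cohort will include pregnancies resulting in a live birth and non-live birth (stillbirth), or spontaneous abortion".
- The Abstract says: "Similar analyses will be conducted for pregnancy complications and outcomes among all eligible pregnancies".
- Section 9.7.2.2 analyses the complications under Secondary Objective 2.

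Section 9.3.2.1 mentions the codes for all three complications under the infant/birth outcomes, and Section 9.3.2.1.7 gives abruption its own entry there. Section 9.3.2.2 then defines the complications again under Secondary Objective 2, each "identified by searching the mother's claims from 20 weeks gestation through the date of delivery".

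On timing, Section 9.3.1 counts a pregnancy as exposed after at least one dose during pregnancy, and Section 9.2.1.2 lets the third-trimester stage run to the end of pregnancy. Section 9.2.1.3 asks comparators to have reached the gestational week of the exposed woman's dose with no prior spontaneous abortion or stillbirth. It does not name complications.

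**The concern.** A programmer who follows 9.7.2 and one who follows Secondary Objective 2 would analyse different women. Section 9.2.1.3 matches the two cohorts separately and Section 9.3.3 fits separate propensity score models, so the matched sets, the comparators and the denominator would all differ.

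The 9.7.2 population is also the less suitable one. The diagnoses sit in the mother's claims, so linking her to an infant adds nothing and costs pregnancies. Abruption and preeclampsia can end in fetal death, so restricting to live births selects on a possible consequence of the outcome. The limitations section (9.9.1) discusses live-birth selection for malformations and other infant outcomes, but not for complications.

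The timing issue is separate and narrower. After a dose given later than 20 weeks, part of the search window has already passed. A complication in that part cannot have been caused by the dose, yet it would count as an exposed outcome.

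**Working it through.** The protocol gives no sample size or precision figure for complications (Section 9.5 covers malformations only), so there is no plan figure to reproduce.

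**1. The population in each place**

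| Place | Population for complications |
|---|---|
| Abstract | all eligible pregnancies |
| Section 8, Secondary Objective 2 | live and non-live births |
| Section 9.2.1 | live birth, stillbirth, spontaneous abortion |
| Section 9.7.2.2 | analysed under Secondary Objective 2, hence that cohort |
| Section 9.7.2 | live births linked to an infant |

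Four places agree and one departs. Sections 9.3.2.1 and 9.3.2.1.7 fix no population, but they place maternal outcomes under an infant heading and so repeat the confusion.

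**2. Cost of requiring linkage**

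Inputs: linkage L of about 74% (Section 9.2.1) or 70-80% (Section 9.9.1). Share of live births lost = 1 - L. If the loss is random, the standard error is multiplied by 1/√L.

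| L | Live births lost | 1/√L | Rise in standard error |
|---|---|---|---|
| 0.70 | 30% | 1.195 | about 20% |
| 0.74 | 26% | 1.162 | about 16% |
| 0.80 | 20% | 1.118 | about 12% |

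For scale, the 711 exposed linked live births of Section 9.5 correspond to 711/0.74, or about 961, exposed live births (889 at 80%, 1016 at 70%). Some 250 (178 to 305) would go unused for outcomes that need no link.

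**3. Cost of requiring a live birth**

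All stillbirths leave the analysis, with any abruption or preeclampsia that preceded them. The documents give neither the stillbirth frequency nor the share of complications that end in stillbirth, so no figure can be attached.

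**4. Share of the search window before the dose**

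Input: the default live-birth gestation of 273 days (Section 9.2.1.1). The window runs from day 140 (20 weeks) to day 273, which is 133 days. For a dose at week w > 20, the share already past is (7w - 140)/133:

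- week 24: 28/133 = 21%
- week 28: 56/133 = 42%
- week 32: 84/133 = 63%
- week 36: 112/133 = 84%

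For any dose up to week 20 the share is 0. These are shares of calendar time, not of events; the documents do not give the timing of complications.

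**5. Effect on a risk ratio**

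Suppose a share f of the baseline complication risk arises before the dose, equally in both groups, and the true risk ratio afterwards is 2.0. The observed ratio is then f × 1 + (1 - f) × 2 = 2 - f. For assumed f of 0.10, 0.25 and 0.50, this gives 1.90, 1.75 and 1.50.

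**The case against.** **It is one stray sentence.** The intended population is clear from four other places, including the analysis section for Secondary Objective 2, and 9.7.2 does not contain the word *only*. This is right about intent. A reader might infer that the complication estimates are bound to be biased. The documents do not support that, because it assumes the outlying sentence overrides the rest. The conflict remains, however: 9.7.2 contrasts the two populations directly, and linked live births is the natural reading of it.

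**The window can be left to the statistical analysis plan.** That plan is not at hand and may tie the window to the dose. But the protocol itself fixes the start and end of the search without reference to the dose. It is fair that few pregnancies may be affected: Section 7 expects very few exposures, mainly in unintended pregnancies, where vaccination may come before the woman knows she is pregnant. Stratifying by stage of pregnancy confines the problem further, without removing it from the late strata.

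**A tempting stronger reading.** A reader might infer that the all-pregnancies cohort is itself wrong, because a spontaneous abortion before 20 weeks cannot have an event searched for only from 20 weeks. The documents do not establish this as an error. They give no frequency of such losses, and a ratio is unaffected if the losses are equally common in both groups. Restricting to pregnancies that reached 20 weeks would condition on a post-exposure event for pre-pregnancy and early doses; that is a choice of estimand. Nor can this dilution be added to the linkage loss: the first arises only in the all-pregnancies cohort, the second only under 9.7.2.

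**Conclusion.** The contradiction over the population stands on the text and should be resolved before the matched cohorts are built. If 9.7.2 were followed, complications ending in stillbirth would be lost (size not estimable from the documents), along with 20-30% of live births. The 12-20% rise in standard errors assumes that linkage failure is unrelated to vaccination and to complications.

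The window point also stands, but only for doses after 20 weeks. With equal pre-dose risk in the two groups it pulls the risk ratio towards 1, and for a safety outcome that weakens a true signal. If a complication alters the chance of being vaccinated, the bias can go either way. The diluted ratios above rest on assumed shares and show scale only.

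Both points concern secondary outcomes. The malformation analysis and its sample size are untouched.

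**What to change.** 1. In Section 9.7.2, state that pregnancy complications are assessed in the separately matched Secondary Objective 2 cohort, meaning all eligible pregnancies, linked or not. Leave the infant/birth outcomes in the linked live-birth cohort.
2. Move the complication text in Sections 9.3.2.1 and 9.3.2.1.7 to Section 9.3.2.2. The abruption definition already stands there, so 9.3.2.1.7 can simply go.
3. In Section 9.3.2.2, start the search at the later of 20 weeks and the vaccination date, and for matched comparators on the same gestational day. Do not count, in either group, a complication coded before that day. Leaving such an event uncounted, rather than removing the woman, keeps the 1:3 matched sets intact.
4. Optionally, add complication prevalence among pregnancies that reached 20 weeks as a supplementary presentation. It should not replace the stated cohort.

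Items 1 and 2 are wording. Item 3 needs modest programming to carry the index day to the comparators. No new data are required.

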Matching with a propensity score will minimize confounding bias due to differences between the HZ/su-exposed and comparator unexposed group. Propensity score matching is discussed below (Sections 9.3.3 and 9.7). Matching on DP, maternal age, and the start date of the pregnancy period, will control for DP differences in HZ/su use, age effects, and potential secular trends in HZ/su use and obstetric outcomes.

[figure not shown]
For each of these study samples, the unit of analysis is a pregnancy episode (Figure 2).

Figure 2 Study schema on study populations for the assessment of infant outcomes and pregnancy outcomes

Panel 1: Study Population for the Assessment of Infant Outcomes

Panel 2: Study Population for the Assessment of Pregnancy Outcomes

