Annex 10 ENCePP Checklist for study protocols

Sect	ion 1: Milestones	Yes	No	N/A	Section	n Number
1.1	Does the protocol specify timelines for					
	1.1.1 Start of data collection ¹	\boxtimes				5
	1.1.2 End of data collection ²	\boxtimes				5
	1.1.3 Progress report(s)			\boxtimes		
	1.1.4 Interim report(s)			\boxtimes		
	1.1.5 Registration in the EU PAS Register®		\boxtimes			
	1.1.6 Final report of study results.	\boxtimes				5
Com	ments:					
Sect	ion 2: Research question		Yes	No	N/A	Section Number
2.1	Does the formulation of the research question and object clearly explain:	ctives	\boxtimes			4, 7, 8, 9
	2.1.1 Why the study is conducted? (e.g. to address an inpublic health concern, a risk identified in the risk management plan, an emerging safety issue)	mportant	\boxtimes			7, 8
	2.1.2 The objective(s) of the study?		\boxtimes			8
	2.1.3 The target population? (i.e. population or subgroup the study results are intended to be generalized)	o to whom	\boxtimes			8, 9.1,
	2.1.4 Which hypothesis(-es) is (are) to be tested?		\boxtimes			4, 9.5, 9.7
	2.1.5 If applicable, that there is no a priori hypothesis?				\boxtimes	
Com	ments:					

¹ Date from which information on the first study is first recorded in the study dataset or, in the case of secondary use of data, the date from which data extraction starts.

² Date from which the analytical dataset is completely available.

	tion 3: Study design	7	'es	No	N/A	Section Number
3.1	3.1 Is the study design described? (e.g. cohort, case-control, cross-sectional, other design)		\boxtimes			9.1
3.2	Does the protocol specify whether the study is based on primary, secondary or combined data collection?		\boxtimes			9.1, 9.4
3.3	Does the protocol specify measures of occurrence? (e.g., rate, risk, prevalence)	, [\leq			9.1
3.4	Does the protocol specify measure(s) of association? (e.g. risk, odd ratio, excess risk, rate ratio, hazard ratio, risk/rate difference, numb needed to harm (NNH))		\boxtimes			9.7.2
3.5	Does the protocol describe the approach for the collection and reporting of adverse events/adverse reactions? (e.g. adverse event that will not be collected in case of primary data collection)	ts [\leq			11
Com	ments:					
Sect	tion 4: Source and study populations	Yes	No	2	N/A	Section
4.1						Number
7.1	Is the source population described?	\boxtimes]		Number 9.1, 9.2

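### Adjustment for residual confounding in the matched cohort depends on a significant univariate test, and no effect measure with a confidence interval is named when that test is not significant

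*Protocol*

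**What the plan says.** Section 9.7.2.1 compares malformation prevalence between vaccinated and unvaccinated matched pregnancies by a Mantel-Haenszel chi-square or Fisher exact test. The regression follows under a condition: "Multivariable conditional logistic regression will be conducted to adjust for potential residual confounding after matching if there is statistical significance in univariate analysis". The abstract has the same condition: "adjust for potential residual confounding after matching if there is statistical significance in univariate analysis". Section 9.7.2.1 applies similar methods to the other infant outcomes. Section 9.7.2.2 extends them to pregnancy outcomes and complications: "Univariate and multivariable statistical analyses will be performed as stated in the primary objective and secondary objective 1".

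Whatever the test shows, Section 9.7.2.1 promises that "the prevalence of MCMs and their associated 95% CIs will be calculated" for the two groups. It names no risk ratio, odds ratio or risk difference. The ENCePP checklist (Annex 10, item 3.4) asks "Does the protocol specify measure(s) of association", answers yes and cites Section 9.7.2.

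The test is not run on a raw cohort. Section 9.2.1.3 matches on Data Partner, maternal age, pregnancy start date and a propensity score, and states: "Matching with a propensity score will minimize confounding bias due to differences between the HZ/su-exposed and comparator unexposed group". Section 9.9.1 nevertheless accepts that residual confounding may remain.

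**The concern.** The protocol's stated purpose for the regression is to deal with imbalance that matching leaves. Such imbalance exists or not whatever the univariate p-value, and it can hide an excess risk as well as create one. Under the rule, a significant result gets the further correction and may be explained by it. A non-significant result never gets it. In a safety study that asymmetry works against finding harm.

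The second issue is what a null result delivers. The study asks whether risk is increased and is sized on a risk ratio of 2.0. A non-significant finding is informative mainly through the upper confidence limit of a ratio. The only model in Section 9.7.2 that yields an association estimate is the conditional one, so the section does not commit to that limit in the case where it matters most.

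**Working it through.** **Inputs.** Section 9.5 gives 711 exposed and 2133 unexposed, 3% reference prevalence, type 1 error 0.05 (sidedness not stated; two-sided assumed), 90% power and a target risk ratio of 2.0.

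**The plan's own figure.** The pooled-variance formula for two proportions, two-sided and without continuity correction, gives 641 exposed for 6% versus 3%. It gives exactly 711 if 2.0 is read as an odds ratio: 2 × (0.03/0.97) = 0.0619 odds, a risk of 5.825%. At 711/2133 a true risk ratio of 2.0 has 92.5% power, so the difference is on the safe side. It does not affect this point; 711/2133 is used below.

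**No true effect.** By definition a nominal 5% test is non-significant, and the model skipped, in about 95% of studies. Simulated rejection rates were 4.3% (chi-square) and 3.75% (Fisher). The interval that such a study could report:

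- Expected events: 711 × 0.03 = 21.3 and 2133 × 0.03 = 64.0.
- SE(log RR) = √(1/21.3 − 1/711 + 1/64.0 − 1/2133) = 0.246.
- 95% CI = exp(±1.96 × 0.246) = 0.62 to 1.62, which excludes 2.0.

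This formula treats the groups as independent; a matched-set analysis would differ somewhat.

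**How often the condition is met.** Power = Φ{[d − 1.96·SE₀]/SE₁}, where d is the risk difference, SE₀ the pooled and SE₁ the unpooled standard error. For an apparent risk ratio of 1.5 (4.5% versus 3%):

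- d = 0.015; pooled risk = (0.045 + 3 × 0.03)/4 = 0.03375.
- SE₀ = √[0.03375 × 0.96625 × (1/711 + 1/2133)] = 0.00782.
- SE₁ = √[0.045 × 0.955/711 + 0.03 × 0.97/2133] = 0.00861.
- Power = Φ[(0.015 − 0.01533)/0.00861] = Φ(−0.038) = 48.5%. Fisher's test, simulated, gives about 43%.

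| Apparent risk ratio | Model is run |
|---|---|
| 1.25 | 17.8% |
| 1.4 | 35.3% |
| 1.5 | 48.5% |
| 1.6 | 61.2% |
| 2.0 | 92.5% |

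**Around the threshold**, with 64 unexposed cases:

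| Exposed cases | RR (95% CI) | Chi-square p | Fisher p | Model |
|---|---|---|---|---|
| 21 | 0.98 (0.61–1.60) | 0.95 | 1.00 | not run |
| 32 | 1.50 (0.99–2.27) | 0.055 | 0.071 | not run |
| 33 | 1.55 (1.03–2.33) | 0.037 | 0.042 | run |

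With 32 exposed cases the interval still contains 2.0, but no adjusted estimate is planned. One more case triggers it.

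**Stage-of-pregnancy strata.** All analyses are also stratified by four stages. If exposure split evenly (assumption: 711/4 ≈ 178 exposed each), the test would be significant only 45% of the time at a true risk ratio of 2.0.

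**The case against.** The strongest reply is that confounding is handled before any test. The comparison follows matching on Data Partner, age and start date, and on a propensity score that includes comorbidities, tobacco, alcohol, obesity, race/ethnicity, region and healthcare encounters (Section 9.3.3), with a primary caliper of 0.01 (Section 9.7.2.3). This stands. A reader might infer that null results receive no confounding control; they do, and only the residual step is conditional. It is not a complete answer, because the protocol itself keeps a model for what matching leaves, and Section 9.2.1.3 permits looser matching (age ±10 years, start date ±120 days, calipers up to 0.2).

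Second, Sections 9.7.2.3 and 9.9.1 promise sensitivity analyses for unobserved confounders, a bounding factor and a comparison with and without poorly captured covariates, none tied to significance. This also stands and softens the consequence. These analyses do not replace a main adjusted estimate, and a bounding factor needs an association estimate to work on.

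Third, the SAP is not shown and may name an effect measure. Section 9.7.3 explicitly rules out further analyses for the descriptive branch; Section 9.7.2 has no such sentence. A reader might infer that no ratio will ever be reported after a null test, and the documents do not support that. A crude ratio could also be derived from the prevalences and group sizes. The condition itself, however, is fixed in the protocol, and Section 9.7.4 says that major changes to primary endpoint analyses would be reflected in a protocol amendment.

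Fourth, the apparent ratio of 1.5 is assumed. Nothing in the documents shows that a true 2.0 would be masked to that value. Removing the condition would help only where the masking came from measured covariates still imbalanced after matching; regression cannot repair unmeasured confounding.

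**Conclusion.** The concern holds in limited form. The condition is stated in the abstract and Section 9.7.2.1 and reaches all outcomes through Section 9.7.2.2. Residual imbalance is therefore corrected only for significant results, and Section 9.7.2 names no effect measure with a CI for a non-significant one, although the checklist cites that section for it.

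Under no effect the model is skipped about 95% of the time, while the data would support a risk-ratio interval of about 0.62 to 1.62. This rests on 3% prevalence in both groups, full recruitment of 711/2133 and a two-sided 5% test. The 48% figure for an apparent ratio of 1.5 shows how the rule behaves and does not forecast masking. The documents do not support the stronger reading that the study leaves null findings unprotected against confounding. Nor would deleting the condition alone yield an adjusted risk ratio, since conditional logistic regression gives an odds ratio.

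**What to change.** Delete "if there is statistical significance in univariate analysis" from the abstract and Section 9.7.2.1; Section 9.7.2.2 then follows by its cross-reference. For the primary outcome and each secondary outcome, state that a named matched effect measure with its 95% CI is always reported: either a risk ratio, or the odds ratio from conditional logistic regression. Report the covariate-adjusted estimate as well whenever event counts allow. Where events are sparse, as with neonatal death or stage-of-pregnancy strata, use a reduced or penalised model, or the matched estimate alone. The choice should depend on event counts and not on a p-value, which also respects the limit on covariates noted in Section 9.9.1. Checklist item 3.4 would then be accurate.

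The sample size does not change. The cost is a short protocol amendment, some extra model runs across the three Data Partners, and imprecise estimates for rare outcomes that will need cautious reading.
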